1.5.2. Partial Response

To satisfy criteria for PR, all of the following conditions must be attained:

- No evidence of new disease
- A \geq 50% decrease from baseline in the SPD of the index nodal and extranodal lesions
- No increase from the nadir in the size of non-index disease
- No increase from the nadir in the size of the liver or spleen and no new liver or spleen enlargement
- If PET performed:
 - Typically FDG-avid lymphoma: if no baseline PET scan or if the PET scan was positive before therapy, the on-treatment PET is positive in ≥ 1 previously involved site– i.e., score of 4 (uptake moderately > liver) or score of 5 (uptake markedly > liver) on the Deauville 5-point scale but with reduced uptake compared with baseline. If baseline PET was performed and was negative, there is no new PET evidence of disease.
 - Variably FDG-avid lymphoma/FDG-avidity unknown: if no pretreatment PET scan or if the pretreatment PET scan was negative for lymphoma, CT criteria should be used in assessing the tumor during treatment. If the PET scan was positive before therapy, the on-treatment PET is positive in ≥ 1 previously involved site.
- Persistence of bone marrow involvement in a subject who meets other criteria for CR based on the disappearance of all nodal and extranodal masses

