8.1.5. Disease Status Assessment for Subjects with NHL

Pretreatment tumor assessments will be performed within 30 days of the first dose of study treatment and will include diagnostic CT scans (with intravenous contrast) or Positron Emission Tomography (PET)/Computerized Tomography Scans (CT scan) for patients with lymphoma, bone marrow aspirate/biopsy, complete blood counts and physical examination. It is anticipated that in most cases the PET/CT scans will be conducted using a single instrument, i.e., as a PET/CT scan (CT scans should be performed using a contiguous reconstruction algorithm of ≤ 5 mm). However, MRI is an acceptable alternative method for assessing disease in subjects

Clinical Study Report 16.1 Study Information Protocol: LAM-002A-NHL-CLN01

Version 9, 18 Feb 2020

who cannot receive intravenous contrast with CT scans. In such subjects MRI and PET scans will have to be obtained separately.

Suitable scans performed prior to screening and within 30 days before first dose may be used for baseline tumor assessments. Similarly bone marrow biopsies/aspirates performed within 2 months prior to first dose may be used for baseline assessments. For subjects with NHL, baseline bone marrow biopsies/aspirates may be omitted if not deemed essential for response assessment or patient management and there is another source of tumor tissue for pretreatment evaluation of gene expression and prognosis. For subjects with CLL/SLL, a baseline bone marrow aspirate is required unless the presence of sufficient circulating cells in the peripheral blood (e.g., $ALC \ge 10 \times 10^9/L$) permits assessment of baseline parameters for gene expression and prognosis. Details of assessments will be collected on the eCRF and must be filed in the subject's medical record.

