1.2. Method of Assessment

Imaging-based evaluation will be used in this study as the primary basis of lymphoma assessment. CT scan is the preferred method for radiographic tumor assessment. Contrastenhanced scanning is preferred, but contrast material may be omitted in subjects for whom use of a contrast agent becomes medically contraindicated or if CT scanning is done in conjunction with PET. If available, PET scan data will be considered in response and progression assessment; however, PET scanning will not be a required component of assessment in this study. As necessary, bone marrow aspirate/biopsy (e.g., for confirmation of CR) or cytological/histological evaluation of lymph nodes, effusions, ascites, or other organ abnormalities) will be also be considered. Clinical palpation, chest x-ray, ultrasound, endoscopy, laparoscopy, radionuclide scan, or tumor markers will not be considered for response assessment. MRI scanning is not advised but may be used at the investigator's discretion in subjects for whom this becomes a necessary alternative to CT scanning.

For radiographic assessments, the same method of assessment and the same technique (e.g., scan type, scanner, subject position, dose of contrast, injection/scan interval) should be used to characterize each identified and reported lesion at baseline and during study treatment and follow-up. CT of the neck, chest, abdomen, and pelvis should be performed with cuts of ≤ 0.5 mm in slice thickness contiguously. If performed, whole-body FDG PET-CT scanning should be extended from the base of the skull to mid-thigh.

All relevant radiographic and clinical information required to make each tumor status assessment must be made available for source verification as requested by the study sponsor.

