1.5.3. Stable Disease

To satisfy criteria for SD, all of the following conditions must be attained:

- No evidence of new disease
- Neither sufficient tumor shrinkage from baseline to qualify for PR nor sufficient evidence of tumor growth to qualify for PD
- If PET-CT performed, the results show a score of 4 (uptake moderately > liver) or score of 5 (uptake markedly > liver) on the Deauville 5-point scale with no significant change in uptake compared with baseline.

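### Appendix 2 requires uptake reduced from baseline for PR even where it admits there is no baseline PET, so a CT responder with a Deauville 4-5 scan on treatment may be unclassifiable at that assessment

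*Combined protocol and SAP*

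**What the plan says.** All places are in the protocol.

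- **PR, typically FDG-avid disease (Appendix 2, 1.5.2).** PR needs every listed condition. If PET is performed, one branch applies "if no baseline PET scan or if the PET scan was positive before therapy". It asks for a positive on-treatment scan with a score of 4, or a "score of 5 (uptake markedly > liver) on the Deauville 5-point scale but with reduced uptake compared with baseline".
- **PR, variably avid or unknown avidity (same section).** Without a pretreatment PET, or with a negative one, "CT criteria should be used in assessing the tumor during treatment". The typically avid branch has no such sentence.
- **SD (1.5.3).** If PET-CT is performed, the score must be 4 or 5 "with no significant change in uptake compared with baseline".
- **When PET is done.** Baseline imaging may be CT or PET/CT (8.1.5 and 11). Appendix 2, 1.2 says "PET scanning will not be a required component of assessment in this study", but also that PET data are considered when available. The same section says "the same method of assessment and the same technique" should be used at baseline and during treatment.
- **Where the classification goes.** ORR counts a best overall response of CR or PR (14.9). NE counts as failure in the full analysis set (14.3.1). The follicular lymphoma boundaries in 14.1.2 count evaluable subjects. Stage 2 evaluability needs assessments that allow a response determination (6.1.5), and non-evaluable subjects may be replaced at the sponsor's discretion (6.13).

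**The concern.** One branch names a subject and then sets a condition that this subject cannot meet. The adjacent sub-bullet shows that the missing-baseline case was foreseen and solved for variably avid disease only.

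Response is assessed by the investigator (5.5), and about 15 expansion sites are planned. Faced with the same scans, one investigator could fall back on CT and call PR, while another could decline to call it. The follicular lymphoma cohorts are monitored subject by subject against fixed response counts, so a single classification can decide whether the boundary is crossed.

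**Working it through.** **1. Can the subject be classified?** Take typically FDG-avid disease, a CT-only baseline, SPD down by at least 50%, and a Deauville 4 or 5 scan on treatment.

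| Category | Result at that assessment |
|---|---|
| CR (1.5.1) | Not met: needs a score of 1 to 3 |
| PR (1.5.2) | Uptake condition cannot be evaluated: no baseline uptake |
| SD (1.5.3) | Same missing comparison; the SPD decrease also already reaches the PR threshold |
| PD (1.5.4) | PET criterion not met: needs increased uptake with anatomic growth |
| NE (1.5.5) | Lists only missing or inadequate images; the general wording in 1.5 (too little information to categorize) could apply |

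The only outlet is the general NE wording. It leads either to a failure (14.3.1) or to possible replacement (6.1.5, 6.13).

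**2. The plan's own figures.** Exact one-sided 95% lower bound for x responses in n: the 5th percentile of Beta(x, n − x + 1).

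- Monotherapy 8/20: bound 21.7%; P(X ≥ 8 | n = 20, ORR 0.20) = 0.032. This agrees with the stated bound of at least 20%.
- Combination 12/20: bound 39.4%; P(X ≥ 12 | n = 20, ORR 0.39) = 0.047. This agrees with the stated bound of at least 39%.

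**3. One lost responder.**

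| Rule at full accrual | Counted as failure | Dropped, before any replacement |
|---|---|---|
| 8/20 (21.7%) | 7/20 = 35.0%, bound 17.7% | 7/19 = 36.8%, bound 18.8% (8/19 needed) |
| 12/20 (39.4%) | 11/20 = 55.0%, bound 34.7% | 11/19 = 57.9%, bound 36.8% (12/19 needed) |

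All four miss. In the right-hand column a replacement who responds would restore 8/20 or 12/20.

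**4. Sensitivity.** The share of true responders lost, m, is not in the documents; 5%, 10% and 20% are assumptions. With true ORR p, the observed response probability is:

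- counted as failures: p(1 − m);
- replaced as non-evaluable: p(1 − m)/(1 − pm).

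Example, p = 0.40 and m = 0.10: 0.40 × 0.90 = 0.360, or 0.360/(1 − 0.04) = 0.375. For p = 0.60: 0.60 × 0.90 = 0.540, or 0.540/(1 − 0.06) = 0.574.

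The probability of ever crossing was computed by exact recursion: add one subject at a time, update the distribution of the response count, and remove the paths that reach the listed count. The monotherapy list gives both 5/11 and 6/11; 6/11 was used.

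| m | Mono, failures | Mono, replaced | Combination, failures | Combination, replaced |
|---|---|---|---|---|
| 0 | 0.679 | 0.679 | 0.684 | 0.684 |
| 5% | 0.614 | 0.640 | 0.587 | 0.645 |
| 10% | 0.546 | 0.597 | 0.486 | 0.602 |
| 20% | 0.405 | 0.503 | 0.295 | 0.504 |

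The replaced columns remove would-be responders only. If would-be SD subjects with the same scan pattern were also replaced, the loss would be smaller.

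**The case against.** A reader might infer that every FDG-avid subject without a baseline PET leaves the ORR numerator. The documents do not support that.

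- The conditions apply only if PET is performed, and PET is optional. A subject followed by CT alone can be PR or SD in the ordinary way.
- CR uses an absolute score and needs no baseline scan. Best overall response is taken across all on-treatment assessments, so a PR at a CT-only visit counts.
- The same-method instruction in Appendix 2, 1.2, and the expectation in 8.1.5 that PET and CT will mostly be done on a single instrument, make a CT baseline followed by an on-study PET less likely. They do not forbid it.

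Nor is PR plainly denied. The section names the no-baseline subject inside the PR definition, which suggests an intention to allow PR. The reduced-uptake phrase can be read as qualifying score 5 only, which would free score 4 but leave score 5 stuck. A strictly literal reading of the list is also awkward elsewhere: its last bullet would make persistent marrow involvement a requirement for every PR.

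It would likewise be too strong to say that one lost PR decides any cohort of 6. The only stated rule there concerns 0/6, so it matters only if that was the cohort's sole response.

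These points stand and narrow the problem. They do not remove it, because intent is not a rule that separate sites will apply alike.

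**Conclusion.** The point holds as an internal contradiction in the response criteria, confined to assessments in typically FDG-avid disease with a Deauville 4-5 on-treatment PET and no baseline PET. It is an ambiguity to repair, not a demonstrated loss of responders.

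The size is unknown and is zero if no subject has that combination of scans. Otherwise one subject can turn a crossed boundary into a missed one. The sensitivity figures rest on assumed loss rates, true ORRs equal to the plan's targets, and the two ways of counting affected subjects. The failure columns are the harsher case, and the plan does not say which treatment applies.

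The conclusion rests on the protocol text. Section 14.2 defers detailed methods to the SAP; a rule there for a missing baseline PET would settle the matter.

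**What to change.** In Appendix 2, 1.5.2 (typically FDG-avid branch) and 1.5.3, apply the comparison with baseline uptake only when a baseline PET exists. When it does not, assign PR and SD by CT criteria, as 1.5.2 already does for variably avid disease. Also state whether an assessment that still cannot be classified counts as a failure or as non-evaluable in the sequential boundaries.

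The cost is about a sentence in each section and no new procedures. Because the study is open-label and responses in follicular lymphoma have already been seen (4.1.4.2), apply the clarified rule to all subjects, including those already assessed, and list any whose best response changes. Requiring a baseline PET wherever on-study PET is planned would also resolve the conflict, but it adds a procedure and does not help subjects already enrolled.

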1.5.3. Stable Disease

To satisfy criteria for SD, all of the following conditions must be attained:

- No evidence of new disease
- Neither sufficient tumor shrinkage from baseline to qualify for PR nor sufficient evidence of tumor growth to qualify for PD
- If PET-CT performed, the results show a score of 4 (uptake moderately > liver) or score of 5 (uptake markedly > liver) on the Deauville 5-point scale with no significant change in uptake compared with baseline.

1.5.4. Progressive Disease

The occurrence of any of the following events indicates progressive disease (PD):

- Evidence of any new disease that was not present at baseline:
 - A new node that measures > 1.5 cm in any diameter
 - A new node that measures > 1.0 cm to ≤ 1.5 cm in the LD and > 1.0 cm in the LPD

- Reappearance of an extranodal lesion that had resolved (i.e., had previously been assigned a PPD of 0 cm²)
- A new extranodal lesion of any size
- New non-index disease (e.g., effusions, ascites, or other organ abnormalities) of any size unequivocally attributable to lymphoma (usually requires PET, biopsy, cytology, or other non-radiologic confirmation to confirm disease attributable to lymphoma). Note: Isolated new effusions, ascites, or bone lesions are not sufficient evidence alone of PD unless histologically confirmed. In patients with no prior history of pulmonary lymphoma, new lung nodules identified by CT are usually benign. Thus, a declaration of PD should not be made if this is the only manifestation of an apparently new lesion.
- New FDG-avid foci consistent with lymphoma rather than another etiology (e.g., infection, inflammation). If there is uncertainty regarding the etiology of new lesions, biopsy or interval scan may be considered.
- New or recurrent bone marrow involvement with lymphoma by PET-CT or by bone marrow biopsy if prior PET-CT or bone marrow biopsy performed as part of the study was negative for lymphoma.
- Evidence of worsening of nodal or extranodal index lesions:
 - Increase from the nadir by $\geq 50\%$ in the SPD of index lesions
 - Evidence of worsening of individual index lymph nodes or nodal masses:
 - Increase from the nadir by $\geq 50\%$ in the PPD for any individual node if the node now has an LD of > 1.5 cm and there is an absolute change from the nadir of ≥ 0.5 cm in the LD or LPD and to an absolute dimension of ≥ 2.0 cm.
 - ➤ Increase from the nadir by $\geq 50\%$ in the LD for any individual node if the node now has an LD of > 1.5 cm and there is an absolute change from the nadir of ≥ 0.5 cm in the LD
 - ➤ Increase from the nadir by $\ge 50\%$ in the LPD for any individual node if the node now has an LPD of > 1.5 cm and there is an absolute change from the nadir of > 0.5 cm in the LPD
 - ➤ If a lesion had been classified as a small lymph node, there is an additional requirement that the lesion has an LD of > 1.0 cm and an LPD of > 1.0 cm
 - Unequivocal increase in the size of non-index disease
 - Unequivocal worsening in the size of the liver or spleen (with the additional condition that there must be ≥ 1 nodule present in the enlarging organ)
- Transformation to a more aggressive NHL histology as established by lymph node biopsy

Version 9, 18 Feb 2020

• If PET performed, there is a score of 4 (uptake moderately > liver) or score of 5 (uptake markedly > liver) on the Deauville 5-point scale with an increase in uptake compared with the nadir in conjunction with an anatomic increase in lesion size consistent with PD.

Note: Study subjects undergoing PET for lymphoma assessment can experience transient disease flare on imaging before having subsequent therapy-induced tumor regression. Worsening of constitutional symptoms or performance status in the absence of objective evidence of worsening lymphoma (e.g., due to infection) may not represent definitive disease progression. Further, transient worsening of disease during temporary interruptions of study therapy (e.g., for drug-related toxicity or inter-current illness) may not indicate definitive progressive lymphoma. If there is uncertainty regarding whether there is true lymphoma progression and if medically appropriate, the subject may continue or resume study treatment and remain under close observation (e.g., evaluated at 3- to 6-week intervals) while relevant radiographic, clinical, and/or laboratory assessments are performed to document whether tumor control can be maintained or whether disease progression has truly occurred. If subsequent evaluations suggest that the subject has experienced persistent definitive disease progression, then the date of progression will be the timepoint at which progression was first objectively documented.

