1.4. Identification and Follow-up of Tumor Lesions and Organomegaly

1.4.1. Index Lesions

Up to 6 lesions (e.g., lymph nodes, liver or spleen nodules, and/or other circumscribed extranodal masses) should be selected as index lesions that will be used to quantitate the status of the disease during study treatment. Ideally, the index lesions should be located in disparate regions of the body and include mediastinal, abdominal, and retroperitoneal areas of disease whenever these sites are involved. For subjects with FDG-avid lymphomas undergoing PET, selection of FDG-avid lesions is preferred.

Index lesions will be measured and recorded at baseline and at the stipulated intervals during treatment. The largest cross-sectional dimensions (i.e., the LD × LPD will be recorded (in cm) for each index lesion. Using the LD and LPD, the product of the perpendicular diameters (PPD) for each index lesion will be calculated. The PPDs and the SPDs for all index lesions will be calculated and recorded. The baseline and nadir PPDs of individual lesions and the baseline and nadir SPDs will be used as references by which objective tumor response and progression will be characterized during treatment. All PPD and SPD measurements will be reported in centimeters squared.

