1.4.3. Extranodal Index Lesions

An extranodal mass may be selected as an index lesion if it is both abnormal and measurable at baseline. An extranodal mass of any size is considered abnormal. It is considered measurable at baseline if it has 2 perpendicular diameters that can be accurately measured in cross section with the LD being ≥ 1.0 cm and the LPD also being ≥ 1.0 cm.

At follow-up timepoints, the PPD of each single extranodal index lesion and the SPD of all extranodal index lesions will be considered. Because extranodal index lesions that have one or both diameters < 0.5 cm and > 0 cm cannot be reliably measured, a default value of 0.5 cm will be assigned for each diameter that meets these criteria and the resulting PPD will be used in SPD calculations. If an extranodal lesion is no longer clearly visible, it will be considered resolved and its PPD will be defined as 0 cm².

If an extranodal lesion that had resolved (i.e., had a PPD of 0 cm²) subsequently reappears, the subject will be considered to have PD. A new extranodal lesion of any size that appears at a site that was not previously involved with lymphoma and is discernible to the radiologist by CT scan will be considered PD.

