2.5.4. Progressive Disease

The occurrence of any of the following events indicates PD:

- Evidence of any new disease:
 - A new node that measures > 1.5 cm in any diameter
 - New splenomegaly as defined in Section 2.4.2
 - New hepatomegaly as defined in Section 2.4.2
 - New non-index disease (e.g., effusions, ascites, or other organ abnormalities related to CLL/SLL)

Note: Isolated new effusions, ascites, or other organ abnormalities are not sufficient evidence alone of PD unless histologically confirmed. Thus, a declaration of PD should not be made if this is the only manifestation of apparently new disease.

- Evidence of worsening of index lesions, spleen or liver, or non-index disease:
 - Increase from the nadir by \ge 50% from the nadir in the SPD of index lesions
 - Increase from the nadir by $\ge 50\%$ in the LD of an individual node or extranodal mass that now has an LD of > 1.5 cm and an LPD of > 1.0 cm
 - Splenic progression as defined in Section 2.4.2
 - Hepatic progression as defined in Section 2.4.2

Version 9, 18 Feb 2020

- Unequivocal increase in the size of non-index disease (e.g., effusions, ascites, or other organ abnormalities related to CLL/SLL)
- Transformation to a more aggressive histology (e.g., Richter syndrome) as established by lymph node biopsy (with the date of the lymph node biopsy being considered the date of CLL/SLL progression if the subject has no earlier objective documentation of CLL/SLL progression)
- Decrease in platelet count or hemoglobin that is attributable to CLL/SLL, is not attributable to an autoimmune phenomenon, and is confirmed by bone marrow biopsy showing an infiltrate of clonal CLL/SLL cells
 - The current platelet count is $< 100 \times 10^9/L$ and there has been a decrease by > 50% from the highest on-study platelet count
 - The current hemoglobin is < 110 g/L (11.0 g/dL) and there has been a decrease by > 20 g/L (2 g/dL) from the highest on-study hemoglobin

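### The NHL progression criteria have no growth rule for a single persisting extranodal index lesion, so on CT such a lesion can more than double and still be scored SD or, in a narrower case, PR

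*Combined protocol and SAP*

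**What the plan says.** All references are to the lymphoma part of Appendix 2 unless stated.

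- **Selection (1.4.1).** Up to six index lesions are chosen. They may be nodes, liver or spleen nodules, or other extranodal masses. On how they are used: "The baseline and nadir PPDs of individual lesions and the baseline and nadir SPDs will be used as references" for judging response and progression.
- **Extranodal follow-up (1.4.3).** "At follow-up timepoints, the PPD of each single extranodal index lesion and the SPD of all extranodal index lesions will be considered".
- **Progression (1.5.4).** The parent item reads "Evidence of worsening of nodal or extranodal index lesions". For index-lesion size it has two branches. One is a rise of at least 50% from nadir "in the SPD of index lesions". The other is "Evidence of worsening of individual index lymph nodes or nodal masses", whose PPD, LD and LPD thresholds are all worded for a node. Elsewhere in the list, extranodal lesions appear only as new lesions or as "Reappearance of an extranodal lesion that had resolved".
- **Partial response (1.5.2).** The size test is a 50% or greater "decrease from baseline in the SPD of the index nodal and extranodal lesions". Growth of non-index disease, liver or spleen rules out PR. No condition concerns growth of one index lesion.
- **Stable disease (1.5.3).** In size terms, this is whatever is neither PR nor PD.
- **CLL/SLL (2.5.4).** Here a single-lesion rule does reach extranodal disease: a rise of at least 50% "in the LD of an individual node or extranodal mass that now has an LD of > 1.5 cm".

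**The concern.** Sections 1.4.1 and 1.4.3 give the single extranodal PPD a role in progression, and the parent item in 1.5.4 announces extranodal lesions. No criterion then uses that PPD. The CLL/SLL list has such a rule, although CLL/SLL index lesions are nodes only (2.4.1) and extranodal lesions there are unmeasured non-index disease (2.4.3). So the rule is present where the lesion is not measured and absent where it is.

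In a mixed response, shrinking or stable nodes can hide a growing extranodal lesion inside the pooled SPD. PD dates feed duration of response and PFS (protocol Section 14.9). PR feeds the objective response rate and the follicular lymphoma accrual boundaries (Section 14.1.2), where one subject can decide the result: for monotherapy 8/20 is on the list and 7/20 is not.

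**Working it through.** The plan states no figure on this point, so there is none to reproduce. The check applies the size rules of 1.5.2 and 1.5.4 as written, on CT alone, with no new disease and no change in non-index disease, liver or spleen.

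**1. When the SPD rule fires.** Let the extranodal lesion hold share f of the nadir SPD, let it grow to m times its nadir area, and let the other lesions stay at nadir. Relative to nadir the SPD is (1 − f) + m·f. PD needs this to be at least 1.5, so m ≥ 1 + 0.5/f.

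| Share f of nadir SPD | Area multiple needed for PD |
|---|---|
| 10% | 6.0 |
| 1/6 (one of six equal lesions) | 4.0 |
| 25% | 3.0 |
| 50% | 2.0 |
| 100% (only index lesion) | 1.5 |

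A doubling therefore escapes PD only when f is below 50%. At exactly 50% it gives +50%, which is PD.

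**2. When PR is still possible.** Let the lesion hold share b of the baseline SPD and double, while the others fall to a fraction r of their baseline. PR needs 2b + r(1 − b) ≤ 0.5, so r ≤ (0.5 − 2b)/(1 − b). At b = 10%, r ≤ 0.3/0.9 = 0.333. At b = 20%, r ≤ 0.1/0.8 = 0.125. At b = 25%, r = 0. A doubled lesion is thus compatible with PR only when its baseline share is below 25% and the rest shrinks strongly.

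**3. Worked cases.** The lesion sizes (cm) are assumed for illustration, and the extranodal lesion is taken to lie outside the liver and spleen.

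| Case | Other index lesions | Extranodal lesion | Total SPD (cm²) | Score as written |
|---|---|---|---|---|
| A | nodes 5×5 and 4×4, falling to 3×3 and 2×2 | 2×2 to 2.9×2.9 (4 to 8.41, ×2.10) | 45 to 21.41 (−52.4%) | PR |
| B | nodes 4×3 and 3×3, stable | 2×2 to 3.5×3 (4 to 10.5, ×2.6) | 25 to 31.5 (+26%) | SD |
| C | as B | 2×2 to 4×4 (4 to 16, ×4.0) | 25 to 37 (+48%) | SD |
| D | five lesions 3×3, stable | 3×3 to 6×5.9 (9 to 35.4, ×3.9) | 54 to 80.4 (+48.9%) | SD |

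In each case, the same growth in a node would be PD. In A, for example, the area is up 110%, the LD is 2.9 cm and the absolute change is 0.9 cm, which meets the single-node PPD criterion.

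**4. Timing in case A.** If this is the first on-study scan, the SPD nadir is the baseline of 45, and PR is recorded despite the growth. If the nodes had shrunk at an earlier scan with the extranodal lesion unchanged, the nadir is 9 + 4 + 4 = 17. The later value of 21.41 is then +25.9%, still not PD. But PR had already been recorded at 17/45 − 1 = −62.2%, so best overall response is PR under either rule and only the PD date moves.

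**5. Single index lesion.** For 2×2 to 2.9×2.9 alone, SPD goes from 4 to 8.41 (+110%), which is PD.

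**The case against.** The strongest reply is that other safeguards exist and that the case needs a discordant response. Much of this limits the point, but none of it closes the gap.

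- **Organ rules.** PR bars growth of the liver or spleen, and enlargement of either organ with a nodule present can be PD (1.4.5, 1.5.4). A nodule can grow without the organ enlarging, and other extranodal sites have no such rule.
- **PET.** Where PET is done, PR in a typically FDG-avid lymphoma with a positive or absent baseline PET requires reduced uptake, and SD requires no significant change in uptake. Rising uptake could therefore block either. This stands, and it confines the clean case to CT-only assessment. But PET is not required (1.2), and its PD item also needs an anatomic increase consistent with PD, for which no extranodal threshold is given.
- **Cited criteria.** Section 1.1 rests on published response criteria that may contain the missing rule. They are not available here, and Appendix 2 is the text that sites will apply.
- **Non-index comparison.** It is tempting to say that index lesions face a weaker test than non-index ones. The contrast is limited, because non-index lesions are not measured and are followed only as present or absent (1.4.4).
- **Weight.** The primary endpoint is DLT (protocol Section 5.4), and PFS and duration of response are descriptive (Section 14.9). This is fair and bears on priority.

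A reader might also infer that inclusion criterion 4, which admits subjects on extranodal disease alone, exposes every NHL cohort. It does not show that: a single index lesion is its own SPD and is caught at +50%. The gap needs at least two index lesions.

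**Conclusion.** The point holds with stated limits. As written, 1.5.4 leaves a persisting extranodal index lesion without a single-lesion progression test, contrary to what 1.4.1 and 1.4.3 lead the reader to expect. With other lesions stable, PD requires 1 + 0.5/f times the nadir area. Growth beyond doubling can be scored SD when the share of nadir SPD is under 50%, and PR when the baseline share is under 25% and the rest shrinks enough. This rests on CT-only assessment, more than one index lesion, and no organ enlargement or new disease.

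Three stronger readings are not supported:

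- **All extranodal growth escapes PD.** It does not; step 1 gives the boundary.
- **The response rate is generally inflated.** Best overall response is the best recorded before PD (1.5), so the response rate and the follicular lymphoma boundaries change only when the growth is present before any PR is recorded. The more usual effect would be a late PD date.
- **Affected subjects must stay on treatment.** Protocol Section 6.12 allows withdrawal for reasons other than documented PD.

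How many subjects are affected cannot be computed, because the documents give neither the frequency of extranodal involvement nor the number of index lesions per subject.

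**What to change.** Reconcile Sections 1.4.1, 1.4.3, 1.5.2 and 1.5.4 of the lymphoma part of Appendix 2:

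- In 1.5.4, make the single-lesion progression criteria expressly cover extranodal index lesions. The sponsor should set the threshold from the response criteria it cites. The node thresholds should not simply be carried over: the appendix treats the two lesion types differently (for instance a default diameter of 1.0 cm for nodes and 0.5 cm for extranodal lesions), and PD is also a ground for stopping study treatment.
- In 1.5.2, add that no individual index lesion may meet the PD criteria of 1.5.4.

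The cost is a wording change in the appendix and a matching change in the response derivation. LD and LPD are already recorded for every index lesion, so no new data are needed. The downside is that a few subjects may move from PR or SD to PD.
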